3.3 Inferential Analyses

Descriptive statistics will be used to summarize the safety and PK data. No formal hypothesis testing is planned.

All analyses (unless otherwise specified) will be performed at a two-sided 10% level of significance.

- Dose Proportionality

Dose proportionality will be evaluated for C_{max} , AUC_{inf} , AUC_t , AUC_{24} (SAD) and steady state parameters AUC_{tau} and $C_{max,ss}$ (MAD). Data will be presented graphically and a statistical analysis using the power model will be conducted. The analysis will be divided into days:

SAD: C_{max} , AUC_{24} , AUC_t , AUC_{inf}

MAD Day 1: C_{max} , AUC_{24}

MAD Day 7: $C_{max,ss}$, AUC_{tau} .

The model will include the \log_e -transformed CVN766 dose level as an independent variable. This model will be used to investigate the null hypothesis ($H_0: \beta=1$). Dose proportionality will be rejected ($H_1: \beta$ not equal 1) if the 90% CI of the estimated slope falls outside the critical interval.

The power model will have the form:

$$Y = a*(dose)^b$$

where Y is the PK parameter, and a and b are the coefficient and exponent, respectively, of the power equation.

By taking the natural logarithm (ln), the power model can be analyzed using linear regression and has the form:

$$\ln(Y) = \ln(a)+b*\ln(dose) + error = \alpha + \beta*\ln(dose) + error,$$

where α is the intercept, and β is the slope, and $\ln(dose)$ is based on the dose size for each subject. Estimates of slope and intercept along with their 90% confidence intervals will be reported. A minimum of 3 values per dose must be available for a given parameter to estimate dose proportionality using the power model. For dose proportionality, the slope of the regression line (b) = 1 and for dose independence $b = 0$.

Apparent dose linearity and proportionality of PK Parameters will be assessed graphically as well. The scatter plots and power model regression line will be plotted together with the natural log-transformed PK parameters as the values on the y-axis, and the natural log-transformed dose level as the values on the x-axis. Regression/scatter plot for SAD and MAD in the log-log scale for the Hummel power analysis will be performed by day.

- Food Effect

The effect of fed/fasting state on PK and bioavailability of CVN766 will be analyzed. The analysis will be descriptively. In addition, a random effects mixed model on the log-transformed pharmacokinetic parameters (AUC_t , AUC_{inf} , AUC_{24} , and C_{max}) will be applied to explore the effect of food, where meal status (fed vs. fasted) will be included as a fixed effect and participant will be included as a random effect. The geometric mean for fed/fasted and their 90% CIs will be estimated from the model based on the least squares means. The ratio of the geometric means (geometric mean ratio) and its 90% CI of the

fed data compared to the fasted data will be obtained based on the exponential of the difference of least-squares means (LSM) from the model.

- Gender Effect

The effect of gender (male vs. female) on Dose Normalized PK parameters of CVN766 will be analyzed. A random effects mixed model on the log-transformed pharmacokinetic parameters:

SAD: C_{\max}/Dose , AUC_{24}/Dose , AUC_t/Dose , $AUC_{\text{inf}}/\text{Dose}$ and $t_{1/2z}$

MAD Day 1: AUC_{24}/Dose , C_{\max}/Dose , AUC_t/Dose , $t_{1/2z}$ and t_{\max} .

MAD Day 7: $C_{\max,ss}/\text{Dose}$, $AUC_{\text{tau}}/\text{Dose}$, AUC_t/Dose , $t_{1/2z}$ and t_{\max} .

will be applied to explore the effect of gender, where gender (male vs. female) will be included as a fixed effect and participant will be included as a random effect. The geometric mean for Male/Female and their 90% CIs will be estimated from the model based on the least squares means. The ratio of the geometric means (geometric mean ratio) and its 90% CI of the Male data compared to the Female data will be obtained based on the exponential of the difference of least-squares means (LSM) from the model.

Point estimates and 90% CIs for differences on the log scale will be exponentiated to obtain estimates for the ratios of geometric means and respective 90% CIs on the original scale.

For $t_{1/2z}$, a non-parametric analysis (Hodges-Lehmann estimate) will be used to produce the median difference between female and male. A p-value will be generated by the Wilcoxon signed-rank test.

3.4 Multiple Comparisons and Multiplicity Adjustments.

Not applicable for this study.

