2.3 Endpoints

Primary endpoint(s)

The primary endpoints of this study will be the following:

- Percentage of subjects who experience at least one treatment-emergent adverse event (TEAE)
- Percentage of subjects with abnormal and clinically significant (CS) safety laboratory test results at least once post-dose
- Percentage of subjects with abnormal and CS electrocardiogram (ECG) test results at least once post-dose
- Percentage of subjects with abnormal and CS vital sign measurements at least once post dose

Secondary endpoints(s)

- Single-dose plasma PK parameters of CVN766 including time to maximum plasma concentration (T_{max}), area under the plasma concentration-time curve from time 0 to 24 (AUC_{24}) and time 0 to infinity (AUC_{inf}), and terminal elimination half-life ($t_{1/2z}$) Multiple-dose plasma PK parameters of CVN766 including C_{min} , C_{trough} , C_{max} , AUC from time 0 to the end of dosing interval (AUC_t), terminal elimination half-life ($t_{1/2z}$), accumulation ratio (R_{acc}), time to steady-state ($T_{ss,max}$), steady-state C_{max} ($C_{max,ss}$), and steady-state C_{min} ($C_{min,ss}$) Single-dose and multiple-dose CSF concentrations and CSF: plasma ratios of CVN766

Other endpoints(s)

- Change from baseline in safety laboratory and ECG test results and vital signs.
- Additional plasma PK parameters of CVN766: CL/F or CL/F_{ss} and Vz/F or Vz/F_{ss}

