10.5 Pharmacokinetic Parameters

Part 1 – Single Ascending Doses

The following pharmacokinetic parameters will, where possible, be determined from the plasma concentrations and CSF of analyte using non-compartmental methods via Phoenix WinNonlin Version 8.3 or higher.

Part 1 – Single Ascending Dose

Parameter	Definition
C_{max}	Observed maximum CVN766 concentration which is directly determined from the plasma concentration time profiles
T_{max}	Time to observed maximum observed CVN766 concentration. If the same C_{max} concentration occurs at different time points, T_{max} is assigned to the first occurrence of C_{max} .
T_{last}	Time to last observed CVN766 concentration.
AUC_{24}	The area under the plasma CVN766 concentration-time curve, from time 0 (time of dosing) to 24 hours, calculated by linear trapezoidal/ linear interpolation method
AUC_t	Area under the drug concentration-time curve, from time 0 (time of dosing) to the last measurable concentration using linear trapezoidal/ linear interpolation method
AUC_{inf}	The area under the plasma CVN766 concentration-time curve from time 0 (time of dosing) extrapolated to infinity. AUC_{inf} is calculated as the sum of AUC_t plus the ratio of the last measurable plasma concentration (C_{last}) to the elimination rate constant (λ_z), calculated by linear trapezoidal/ linear interpolation method.
$AUC_{\%extrap}$	The percentage of the AUC that has been extrapolated beyond the last observed data point, using the following formula, calculated by linear trapezoidal/ linear interpolation method $AUC_{\%extrap} = (AUC_{inf} - AUC_t) / (AUC_{inf}) * 100$
λ_z	Apparent terminal elimination rate constant calculated by linear regression of the terminal linear portion of the log concentration vs. time curve.
$t_{1/2}$	Apparent plasma terminal half-life calculated as $\ln(2) / \lambda_z$
CL/F	Apparent total plasma clearance, using the following formula $Dose / AUC_{inf}$
V_z/F	Apparent volume of distribution based on the terminal phase, reported to 3 significant figures and calculated as: $Dose / (\lambda_z \times AUC_{inf})$.
CSF:Plasma ratio	Ratio of the CVN766 concentration in CSF vs. the CVN766 concentration in plasma at 3h post dose.
DN_ C_{max}	Dose-normalized $C_{max} = C_{max} / dose$
DN_ AUC_{24hr}	Dose-normalized $AUC_{24hr} = AUC_{24hr} / dose$
DN_ AUC_t	Dose-normalized $AUC_t = AUC_t / dose$

DN_AUC _{inf}	Dose-normalized AUC _{inf} = AUC _{inf} /dose
-----------------------	---

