Summary of Plasma PK parameters

PK parameters will be determined for each analyte with intensive PK samplings. For the purpose of calculating the non-compartmental PK parameters, concentrations that are BLQ prior to the first measurable concentration value will be set equal to zero. BLQ values embedded between measurable concentrations will be set to missing. Concentrations that are BLQ in the terminal phase after the last measurable concentration will be set to missing.

It should be noted the imputation of BLQ for the determination of PK parameters is different from the BLQ imputation when PK concentrations are summarized. When PK parameters are estimated by a standard non-compartmental model, actual collection time will be used in the calculation of plasma PK parameters.

Goodness of Fit

- If data permits, the default ‘best fit’ method by Phoenix WinNonlin will be used for the selection of slopes to determine ‘ λ_z ’. If data do not permit, then the slope selection will be done by visual inspection or by a manual method to determine λ_z .
- When assessing terminal elimination phases, the R^2 adjusted value will be used as a measure of the goodness of fit of the data points to the determined line.
- Regression-based parameters (λ_z or k_{el} , AUC_{inf} , $AUC\%_{extrap}$, $t_{1/2}$, CL/F or CL/Fss, and V_z/F or V_z/F_{ss}) will only be calculated if the R^2 adjusted value of the regression line is greater than or equal to 0.8. If regression-based parameters cannot be calculated, they will be set to “NC”, defined as “not calculated” in the data listings and summary tables as appropriate.

Calculation of AUC

- The minimum requirement for the calculation of AUC will be the inclusion of at least 3 consecutive plasma concentrations above the lower limit of quantification (LLOQ), with at least one of these concentrations following C_{max} .
- All AUC values will be calculated using linear trapezoidal/ linear interpolation method

Period of Estimation

- Time period used for the estimation of $t_{1/2}$, where possible, will be over at least 2 half lives.
- Where an elimination half-life is estimated over a time period of less than 2 half-lives, it will be flagged in the data listings at the discretion of the pharmacokineticist, and the robustness of the half-life value and regression-based parameters (λ_z or k_{el} , AUC_{inf} , $AUC_{\%extrap}$, $t_{1/2}$, CL/F or CL/F_{ss} , and V_z/F or V_z/F_{ss}) should be discussed in the study report.

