Source Listing: 16.2.6.4.1
Add following treatment;
CVN766 45 mg
Include Visit = Day 1 and Day 7

Table 14.2.6.1 Statistical Analysis of Dose Proportionality for CVN766 SAD (Pharmacokinetic Population)

Analyte: xxxx

Parameter	n	Intercept Estimate	Slope	
			Estimate	90% CI
AUC _{inf}	xx	x.xx	xxx.xx	(x.xx, x.xx)
AUC _t	xx	x.xx	xxx.xx	(x.xx, x.xx)
AUC ₂₄	xx	x.xx	xxx.xx	(x.xx, x.xx)
C _{max}	xx	x.xx	xxx.xx	(x.xx, x.xx)

Source Listing: 16.2.6.3.1
 CI = Confidence Interval.
 Power Model: Ln(PK)=intercept + Ln(dose)

Dose proportionality can generally be concluded if the 90% CIs around the slope estimate (i.e., β1) include the value of 1 and is supported by the descriptive and graphical interpretation.

Programming Note:
 Include only the following cohorts;
 CVN766 5 mg, CVN766 15 mg, CVN766 45 mg(Fasted), CVN766 125 mg, CVN766 250 mg.

Table 14.2.6.2 Statistical Analysis of Dose Proportionality for CVN766 MAD (Pharmacokinetic Population)

Analyte: xxx
 Day 1

Parameter	n	Intercept Estimate	Slope	
			Estimate	90% CI
AUC ₂₄	xx	x.xx	xxx.xx	(x.xx, x.xx)
C _{max}	xx	x.xx	xxx.xx	(x.xx, x.xx)

Source Listing: 16.2.6.3.2
 CI = Confidence Interval.
 Power Model: Ln(PK)=intercept + Ln(dose)

Analyte: xxx
 Day 7

Parameter	n	Intercept Estimate	Slope	
			Estimate	90% CI
AUC _{tau}	xx	x.xx	xxx.xx	(x.xx, x.xx)
C _{max,ss}	xx	x.xx	xxx.xx	(x.xx, x.xx)

Source Listing: 16.2.6.3.2
 CI = Confidence Interval.
 Power Model: Ln(PK)=intercept + Ln(dose)

Dose proportionality can generally be concluded if the 90% CIs around the slope estimate (i.e., β_1) include the value of 1 and is supported by the descriptive and graphical interpretation.

Table 14.2.7.1 Food Effect Assessment of Plasma CVN766 Pharmacokinetic Parameters SAD(Pharmacokinetic Population)

Analyte:xxxx

Parameter (Unit)/ Statistics	CVN766 45 mg Fasted (N=xx)	CVN766 45 mg Fed (N=xx)
AUC _t (Unit)		
n	xx.xx	xx.xx
Geometric LS Mean (90% CI)	xx.xx (xx.xx, xx.xx)	xx.xx (xx.xx, xx.xx)
Ratio of Geometric LS Means (Fed/Fasting)		xx.xx
90% CI for Ratio of Geometric LS Means (Fed/Fasting)		(xx.xx, xx.xx)
AUC _{inf} (Unit)		
n	xx.xx	xx.xx
Geometric LS Mean	xx.xx	xx.xx
Ratio of Geometric LS Means (Fed/Fasting)		xx.xx
90% CI for Ratio of Geometric LS Means (Fed/Fasting)		(xx.xx, xx.xx)
AUC ₂₄ (Unit)		
n	xx.xx	xx.xx
LS Mean (SE)	xx.xx (xx.xxx)	xx.xx (xx.xxx)
Geometric LS Mean (90% CI)	xx.xx (xx.xx, xx.xx)	xx.xx (xx.xx, xx.xx)
Ratio of Geometric LS Means (Fed/Fasting)		xx.xx
C _{max} (Unit)		
n	xx.xx	xx.xx

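### The SAD dose-proportionality test on AUC_t uses an integration window set by the assay limit; if low-dose profiles fall below it before 72 h, the slope is biased above 1 even when kinetics are proportional.

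*SAP*

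**What the plan says.** Section 3.3 opens the analysis with "Dose proportionality will be evaluated for" a list that, for SAD, holds C_max, AUC_24, AUC_t and AUC_inf. Section 10.7 repeats the list, and the shell of Table 14.2.6.1 has a row for each. None is ranked above the others. For MAD, the tested lists omit AUC_t.

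The hypothesis is beta = 1 against beta not equal to 1: "This model will be used to investigate the null hypothesis". Analyses "will be performed at a two-sided 10% level of significance". Section 3.3 rejects proportionality "if the 90% CI of the estimated slope falls outside the critical interval", but never gives that interval. The Table 14.2.6.1 shell has a softer rule: proportionality can generally be concluded if the 90% CIs "include the value of 1 and is supported by the descriptive and graphical interpretation". Section 3.3 also says that no formal hypothesis testing is planned.

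Section 10.5 defines single-dose AUC_t as the area from dosing "to the last measurable concentration using linear trapezoidal/ linear interpolation method". For the parameter calculation, Section 10.7 adds: "Concentrations that are BLQ in the terminal phase after the last measurable concentration will be set to missing". Doses run from 5 to 250 mg (Section 2.1.1), and all SAD cohorts share one sampling schedule ending at 72 h (Section 10.1).

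**The concern.** A power-model slope measures dose proportionality only if the response covers the same part of the profile at every dose. AUC_t need not do so. Its upper limit is the last sample above the LLOQ, and over a 50-fold dose range that limit can come much earlier at 5 mg than at 250 mg. A larger share of the true area is then missing at the low doses, and the regression reads this as exposure rising faster than dose.

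The bias has one direction, upward. It can produce an apparent finding of more-than-proportional exposure in a first-in-human study, and it can partly hide a true slope below 1. The SAP does not say which parameter governs if the AUC_t row disagrees with the others.

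**Working it through.** **Inputs from the SAP.** Doses 5, 15, 45, 125 and 250 mg; 6 active subjects per dose, so N = 30 (optional cohort S3a not counted); sampling at 0.5 to 72 h; linear trapezoids; BLQ values after the last measurable one set to missing; two-sided 10% level.

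**Inputs not in the SAP, assumed and varied.** LLOQ relative to the 5 mg peak (r = LLOQ/peak, so a ratio of 5 is r = 20%), half-life, and between-subject CV. Rejection means that the 90% CI excludes 1.

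**The plan's own figure.** With x = ln(dose), the mean of x over the five doses is 3.695 and the sum of squared deviations is 9.956. With 6 subjects per dose, Sxx = 6 × 9.956 = 59.74. The critical value is t(0.95, 28 df) = 1.701. If the true slope is 1 and nothing is truncated, the 90% CI excludes 1 in exactly 10% of trials, as stated.

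**Closed form for truncation.** For a mono-exponential decline, the area beyond the last measurable point is LLOQ/λz and the whole area is peak/λz. Under proportional kinetics

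AUC_t/AUC_inf = 1 − r × 5/dose.

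The slope bias is Σ(x − x̄) ln(1 − r × 5/dose) / Σ(x − x̄)².

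For r = 20%, the retained fractions at the five doses are 0.800, 0.933, 0.978, 0.992 and 0.996, with logs −0.223, −0.069, −0.023, −0.008 and −0.004. The numerator is 0.515, so the bias is 0.515/9.956 = 0.052 and the expected slope is 1.052. At CV 30%, σ = √ln(1.09) = 0.294 and SE = 0.294/√59.74 = 0.038. The noncentrality is 0.0517/0.0380 = 1.36, and the noncentral t gives 38% rejection.

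| r (5 mg peak/LLOQ) | Expected slope | Rejection at CV 20 / 30 / 50% |
|---|---|---|
| 1% (100) | 1.002 | 10 / 10 / 10% |
| 5% (20) | 1.012 | 14 / 12 / 11% |
| 10% (10) | 1.02 | 24 / 17 / 13% |
| 20% (5) | 1.052 | 63 / 38 / 21% |
| 30% (about 3) | 1.082 | 93 / 68 / 37% |

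**Simulation at the SAP sampling times.** These runs used a one-compartment oral model with exactly proportional kinetics and the SAP's BLQ rules, at CV 30%, with 200 to 600 trials per setting where recorded.

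- Ratio 5, half-life 6 to 12 h: most runs gave 33-38% rejection with mean slope 1.06 to 1.07. One set gave 42% (6 h) and 49% (12 h). In its 12 h case, median T_last was 24 h at 5 mg and 72 h at 250 mg.
- Ratio 10, half-life 6 to 12 h: 15-20% in most runs, with one result at 24%.
- Ratio 10, half-life 24 h: 12-14%.
- Ratio 50: 12%, mean slope 1.01. At ratio 100 and above: slope 0.997 to 1.008, rejection about 10-12%.

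**Do the alternatives escape?**

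- C_max stayed at 8-13% throughout.
- AUC_24 stayed near nominal (about 7-13%) when λz completed the interval. If it is simply stopped at a T_last below 24 h, rejection at half-life 6 h was 22% at ratio 5 and 47% at ratio 3.
- AUC_inf, kept only where extrapolation was at most 20%, never reached the SAP's minimum of 3 values per dose at ratio 3 (half-life 6 h). At ratio 5 it did so in 19-49% of trials, depending on half-life and run, with mean slope 0.94 to 0.97.
- An area to one common time quantifiable at every dose kept the slope at 0.99 to 1.00 and rejection at 7-12% in every setting run.

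**The case against.** The strongest reply is that the effect is conditional. The SAP does not say that 5 mg profiles reach the LLOQ early. If all doses stay measurable to 72 h, AUC_t has one common window and no such bias. The footnote to Table 7 leaves open a half-life above 15 h, which weakens the effect. This stands: a reader might infer that the AUC_t slope is certainly wrong, and the document does not support that.

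Three other stronger readings also fail.

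- *AUC_24 and AUC_inf are clean replacements as written.* Section 10.5 gives no rule for AUC_24 when T_last is below 24 h, and AUC_inf is often missing or biased downward where truncation is heavy.
- *AUC_t should go because it is not a named single-dose endpoint.* Section 2.3 names "area under the plasma concentration-time curve from time 0 to 24" and AUC to infinity, but its list is introduced as non-exhaustive and also omits C_max.
- *AUC_t plays no part in MAD proportionality.* It is absent from the MAD tests, but the MAD AUC_t figure takes over the power-model curve.

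The consequence is also limited. The analysis is described as not formally confirmatory, the shell asks for descriptive and graphical support, and no escalation rule or primary endpoint in the SAP depends on this slope. T_last is summarised by dose in Table 14.2.4.1, so a careful reader could explain a discordant row. But Section 3.3 still states a null hypothesis and a rejection rule. The AUC_t figure would show the same truncation, and nothing ties the AUC_t result to T_last or ranks the parameters.

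**Conclusion.** The point holds in conditional form. By the SAP's own definitions, LLOQ truncation before 72 h at low doses makes the AUC_t window depend on dose and pushes the slope above 1 under proportional kinetics. At CV 30% and half-life 6 to 12 h, the nominal 10% rejection rate becomes about 35-40% at a 5 mg C_max of 5 times the LLOQ, and about 15-20% at 10 times (12-14% with half-life 24 h). It is close to nominal at about 50 times, or if every dose stays measurable to 72 h. Larger CVs dilute the effect and smaller ones sharpen it.

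Which case applies cannot be settled from the SAP. The rates also depend on the CI-excludes-1 reading, because the critical interval in Section 3.3 is not given. The change is worth making because the bias has one direction and the remedy uses data already planned; the study's primary conclusions are not at risk.

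**What to change.** Do not base the SAD proportionality conclusion on the AUC_t slope. Change Sections 3.3 and 10.7, Table 14.2.6.1 and the regression line in Figure 14.2.3.4.1. Treat the MAD AUC_t figure likewise (14.2.3.4.2 in the shells, 14.2.3.5.2 in the Section 16 list).

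- Keep AUC_t in the descriptive tables and show it with T_last by dose.
- Base the conclusion on C_max and an AUC to one common nominal time quantifiable at all dose levels. AUC_24 can serve where T_last reaches 24 h or the interval is completed with λz; state that rule.
- Use AUC_inf where enough subjects meet the extrapolation criterion at every dose.
- Give the critical interval, or adopt the shell's rule in Section 3.3.

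The cost is a few SAP edits and no new data. AUC_t loses its customary inferential row, and the common time must be chosen by a rule set before unblinding.

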3. STATISTICAL CONSIDERATIONS

Data will be handled and processed per the sponsor's representative (Novotech) Standard Operating Procedures (SOPs), which are written based on the principles of good clinical practice (GCP).

Each study part will be presented separately.

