12. CHANGES TO THE PLANNED ANALYSIS

Changes to planned analysis include:

- The following endpoint has been added in relation to PK analysis: To potentially identify significant difference between gender of PK parameters in plasma.
- Standard descriptive stats for HR, sBP and dBP postural data will be reported using a categorical tabulation for number (percentage) of subjects per time point in relation to:
 - Drop in dBP of ≥ 10 mmHg when moving from supine to standing
 - Drop in sBP of ≥ 20 mmHg when moving from supine to standing
 - Increase in HR of ≥ 30 bpm when moving from supine to standing
- For triplicate vital sign at Day -1/ baseline average value will be used.
- Pharmacodynamic Exploratory Endpoints will not be included in the SAP.
- To date, RNA/DNA Analysis has not been conducted, and no data is available for the SAP.
- No suicidal assessments were conducted as part of this study; therefore, this will not be included in data listings.
- It was decided that screen failure data will not be entered in the EDC, as it is the site/CRO practice for phase 1 studies because there are hundreds of SFs, and this data is not imperative for any analysis.

- **INTERIM AND FINAL ANALYSIS**

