Geometric LS Mean (90% CI)	xx.xx (xx.xx, xx.xx)	xx.xx (xx.xx, xx.xx)
Ratio of Geometric LS Means (Fed/Fasting)		xx.xx
90% CI for Ratio of Geometric LS Means (Fed/Fasting)		(xx.xx, xx.xx)

Source: Listing 16.2.6.3.1

LS = Least Square, SE = Standard Error, CI = Confidence Interval.

Programming Note:

- ANOVA model will be used
 - Fixed Effect: food status (fed, fasted)

Sponsor: Cerevance Gamma, Inc.
Protocol: CVN766-101

Data Cut-Off: 2022-10-26

- Random Effect: Subject

Table 14.2.8.1 Gender Effect Assessment of Plasma CVN766 Dose Normalized Pharmacokinetic Parameters SAD (Pharmacokinetic Population)

Analyte:xxxx
 Visit: Day 1

Treatment	Parameter	Statistics	Gender	
			Male	Female
Pooled CVN766	AUC24/Dose	n	xx	xx
		Geometric LS mean (90% CI)	xx.xx (xx.xx, xx.xx)	xx.xx (xx.xx, xx.xx)
		Geometric mean ratio(90% CI) (female vs male)		xx.xx (xx.xx, xx.xx)
	Cmax/Dose	n	xx	xx
		Geometric LS mean (90% CI)	xx.xx (xx.xx, xx.xx)	xx.xx (xx.xx, xx.xx)
		Geometric mean ratio(90% CI) (female vs male)		xx.xx (xx.xx, xx.xx)
	AUCt/Dose	n	xx	xx
		Geometric LS mean (90% CI)	xx.xx (xx.xx, xx.xx)	xx.xx (xx.xx, xx.xx)
		Geometric mean ratio(90% CI) (female vs male)		xx.xx (xx.xx, xx.xx)
	AUCinf/Dose	n	xx	xx
		Geometric LS mean (90% CI)	xx.xx (xx.xx, xx.xx)	xx.xx (xx.xx, xx.xx)
		Geometric mean ratio(90% CI) (female vs male)		xx.xx (xx.xx, xx.xx)
	Tl/2z	n	xx	xx
		Geometric LS mean (90% CI)	xx.xx (xx.xx, xx.xx)	xx.xx (xx.xx, xx.xx)
		Geometric mean ratio(90% CI) (female vs male)		xx.xx (xx.xx, xx.xx)
	Tmax	n	xx	xx
		Hodges-Lehmann estimate (Median)	xx.xx	xx.xx
		Hodges-Lehmann CI		xx.xx (xx.xx, xx.xx)

Source: Listing 16.2.6.3.1
 LS = Least Square, SE = Standard Error, CI = Confidence Interval.

Programming Note:

- ANOVA model will be used
 - Fixed Effect: Gender (Male, Female)
 - Random Effect: Subject

Programming Note:
 Include only the following cohorts;
 CVN766 5 mg, CVN766 15 mg, CVN766 45 mg(Fasted), CVN766 125 mg, CVN766 250 mg

Table 14.2.8.2 Gender Effect Assessment of Plasma CVN766 Pharmacokinetic Parameters MAD (Pharmacokinetic Population)

Analyte:xxxx
 Day 1

Treatment	Parameter	Statistics	Gender	
			Male	Female
Pooled CVN766	AUC24/Dose	n	xx	xx
		Geometric LS mean (90% CI)	xx.xx (xx.xx, xx.xx)	xx.xx (xx.xx, xx.xx)
		Geometric mean ratio(90% CI) (female vs male)		xx.xx (xx.xx, xx.xx)
	Cmax/Dose	n	xx	xx
		Geometric LS mean (90% CI)	xx.xx (xx.xx, xx.xx)	xx.xx (xx.xx, xx.xx)
		Geometric mean ratio(90% CI) (female vs male)		xx.xx (xx.xx, xx.xx)
	AUCt/Dose	n	xx	xx

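### The gender-effect model carries a participant random effect with one value per participant, and pools dose-normalised exposure across doses with no dose term

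*SAP*

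**What the plan says.** Section 3.3 introduces the analysis thus: "The effect of gender (male vs. female) on Dose Normalized PK parameters of CVN766 will be analyzed". The model is a mixed model on the log scale, "where gender (male vs. female) will be included as a fixed effect and participant will be included as a random effect". No dose or cohort term is named.

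The programming notes to mock Tables 14.2.8.1 (SAD) and 14.2.8.2 (MAD) repeat this: "Fixed Effect: Gender (Male, Female" and "Random Effect: Subject". The SAD table has one pooled active group, "Pooled CVN766", and its note restricts the data to "CVN766 5 mg, CVN766 15 mg, CVN766 45 mg(Fasted), CVN766 125 mg, CVN766 250 mg". The fed period of Cohort S3 is therefore left out. Section 3 says "Each study part will be presented separately", and within MAD both Section 3.3 and the table keep Day 1 and Day 7 apart.

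Section 12 lists the analysis as an addition made by the SAP: "To potentially identify significant difference between gender of PK parameters in plasma".

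**The concern.** A participant random effect needs repeated values within a participant. The food-effect model, described just before in Section 3.3, has them (fasted and fed). The gender model takes over the same structure but has one value per participant, so the between-participant and residual components describe the same variation.

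The second issue is dose. Dividing exposure by dose removes the dose effect only if the power-model slope is exactly 1. The dose-proportionality analysis in Section 3.3 treats that as a hypothesis to examine, while the gender model takes it as given. If the slope differs from 1, a dose trend stays in the pooled data. It adds to the residual variance, and it shifts the sex ratio when men and women are spread differently over the doses. At stake are the geometric mean ratios and 90% CIs in the two gender tables.

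**Working it through.** The SAP gives no figure of its own for this analysis, so there is none to reproduce.

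**Inputs from the SAP.** Six active participants per cohort (Section 2.5), so 5 × 6 = 30 in SAD and 3 × 6 = 18 in MAD. SAD doses 5, 15, 45, 125, 250 mg, a range of 250/5 = 50-fold. MAD doses 45, 125, 250 mg, a range of 250/45 = 5.6-fold. Intervals are 90%.

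**Assumptions, not in the SAP.** Power-model slope β (0.8, with others for range), between-subject CV 40%, and the sex mix by cohort.

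**1. Participant term.** Let X hold the intercept and gender, and Z the participant indicators. With one value each, Z is the identity matrix:
- SAD: rank[X Z] = 30 with N = 30, leaving 0 residual df.
- MAD: rank[X Z] = 18 with N = 18, leaving 0.

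In an illustrative data set of 30, giving 0, 25, 50, 75 or 99% of the variance to participant left the REML log-likelihood at 13.357076, the gender coefficient at 0.1481 and its SE at 0.1248 every time. Only the split is undetermined. Without the random effect the df are 30 − 2 = 28 and 18 − 2 = 16. The SAP names no df method. The multiplier is t = 1.70 at 28 df, and would be 6.31 if software fell back to 1 df.

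**2. Dose trend left after normalisation.** Top-to-bottom ratio = (dose range)^(β−1).
- SAD: 50^(−0.2) = 0.46 at β = 0.8 (0.31 at 0.7; 0.68 at 0.9; 2.19 at 1.2).
- MAD: 5.556^(−0.2) = 0.71 at β = 0.8.

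**3. Precision.** The log-SD for CV 40% is √ln(1.16) = 0.385. The variance of ln(dose) is 1.991 in SAD and 0.496 in MAD. Without a dose term the SD at β = 0.8 becomes:
- SAD: √(0.385² + 0.2² × 1.991) = 0.478.
- MAD: √(0.385² + 0.2² × 0.496) = 0.410.

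The CI factor (the multiplier either side of the ratio), with equal numbers of each sex balanced over doses, is exp(t × SD × √(4/n)):

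| | No dose term | With ln(dose) |
|---|---|---|
| SAD | exp(1.701 × 0.478 × 0.365) = 1.345 | exp(1.703 × 0.385 × 0.365) = 1.271 |
| MAD | exp(1.746 × 0.410 × 0.471) = 1.402 | exp(1.753 × 0.385 × 0.471) = 1.375 |

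If each participant's sex is instead drawn at random (50:50; 20,000 simulated trials), sex is partly confounded with dose and the average factors are about 1.35 against 1.28 in SAD and 1.41 against 1.40 in MAD.

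**4. Bias for a given sex mix.** Spurious female/male ratio = exp((β − 1) × difference in mean ln(dose), women minus men). With 4, 4, 3, 2, 2 women of 6 from the lowest to the highest SAD dose, the means are 3.293 and 4.097, a difference of −0.804. At β = 0.8 the ratio is exp(−0.2 × −0.804) = 1.17. It is 1.27 at β = 0.7, 1.08 at 0.9 and 0.85 at 1.2. In MAD with 4, 3, 2 women it is 1.08 at β = 0.8. It is 1.00 if β = 1 or if sex is balanced over doses.

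**5. Coverage.** In the same simulation with no true sex effect, the 90% CI from the unadjusted model (no random effect) covered the truth in about 90% of trials for slopes from 0.7 to 1.

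**The case against.** The case for leaving the model alone has real substance.

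- A reader might infer that the gender effect cannot be estimated. It can: the ratio and its SE depend only on the total variance. The df or convergence problem is a possibility, not a demonstrated result.
- A reader might infer that any departure from proportionality produces false sex effects. On average over random sex allocation it does not, since the leftover dose trend enters the residual and the interval widens to match. Bias arises only in a trial whose realised sex mix differs across doses, and the SAP does not give the sex mix.
- A reader might blame a lack of stratification by sex. The document does not support that: such detail may be in the protocol, and stratifying within a cohort would not balance sex across successive dose cohorts.
- Nothing in the SAP suggests that exposure is non-proportional, and the planned plots of dose-normalised parameters against dose (Section 16) would show it. The analysis is exploratory and informs no primary or secondary endpoint.

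These arguments limit the consequences. They do not justify a participant term with single records, or assuming a slope that is under test. Single records in SAD do rest on the fasted-only table note, because Section 3.3 itself does not exclude the fed data. If those were included, only the 6 active S3 participants would have two records, and the model would then lack a meal term.

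**Conclusion.** The point holds as a modest specification fault. The participant random effect does not suit the data structure and should go, though the gender ratio survives it. The missing dose term costs precision if the slope is not 1: noticeably in SAD (about 1.35 against 1.28) and hardly at all in MAD (1.41 against 1.40). It also exposes the ratio to bias under a realised sex imbalance over doses (1.17 in the SAD example). These sizes rest on the assumed slope of 0.8, CV of 40% and sex mixes; with a slope of 1 both effects vanish. The dose part does not concern t1/2z or tmax, which are not dose-normalised. No primary result is affected.

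**What to change.** In Section 3.3, for the exposure parameters, delete the participant random effect and specify an ordinary linear model, ln(parameter) = sex + ln(dose), fitted separately for SAD (fasted), MAD Day 1 and MAD Day 7. Report the sex geometric mean ratio with its 90% CI, labelled exploratory. State the fasted-only restriction in the text as well, and change the notes to Tables 14.2.8.1 and 14.2.8.2 to match. With ln(dose) in the model the sex ratio is the same whether or not the response is divided by dose, since ln(parameter/dose) = ln(parameter) − ln(dose) only shifts the slope by 1.

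The cost is wording and 1 df (28 to 27 in SAD, 16 to 15 in MAD). If exposure is proportional, the CI factor under random sex allocation goes from 1.273 to 1.279 in SAD and from about 1.38 to 1.40 in MAD.
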